3.5.3 Single Agent Dose escalation decisions (Part A, Arm 1)

Patients treated during the Part A, Arm 1 dose escalation phase of the trial who either receive four administrations of BI-1206 or experience a DLT will be evaluable for dose escalation and/or cohort expansion decisions in Part A, Arm 1.

Patients who receive less than 80% of their total planned induction doses (total across the four administrations) but complete the DLT period (Week 5) are not evaluable for dose escalation decisions (unless they have experienced a DLT).

Data from all patients who receive less than 4 doses of BI-1206 (single agent) and any available data from Part A, Arm 2 (if opened) will also be reviewed and taken into consideration at dose decision meetings. Data from any other trials investigating BI-1206 will also be considered in the dose escalation decisions.

For patients who do not receive the total full dose, please see [Section 6.2.5.6](#) for decision making on continuation of treatment. [Section 5.9.6](#) 'Dose delays/treatment discontinuation' also offers guidance for re-challenging patients post related AE observation.

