^a Assumes that no clinically relevant ≥Grade 2 related toxicity has occurred

^b Assumes that no DLTs are encountered and is also dependant on number of patients that need to be replaced (if patient withdraws for reasons other than DLT).

5.4.1 Action if DLT observed in Cohort 1 (0.4mg to 50 mg), Part A Arm 1

Cohort 1 will consist of a minimum of a single patient, with intra patient dose escalation permitted up to a maximum weekly dose of 50 mg. Safety data will be reviewed on a weekly basis prior to the next planned dose and a decision to dose-escalate will be made based on this data.

If a DLT is observed at or below a dose of 50 mg the cohort will be expanded to up to six patients at the dose level at which the DLT is first identified (the most recent dose prior to onset of the event identified as a DLT). If one out of the six patients experiences DLT, intra-patient dose escalation will cease but standard dose escalation will continue; subsequent cohorts will be expanded to three patients. If two or more out of the six patients experiences a DLT, decisions about future patients will be made in accordance with Figure 4.

5.4.2 Dose escalation and action if clinically relevant \geq Grade 2 related toxicity observed at dose levels from Cohort 2 onwards, Part A Arm 1

From Cohort 2 onwards, all cohorts will include a minimum of one patient (see Figure 4)

- In the first patient recruited, any episode of clinically relevant \geq Grade 2 related toxicity would trigger cohort expansion to a minimum of 3 patients.
- Clinical relevance of the related toxicity will be determined by review and agreement between the relevant Investigator, Chief Investigator and Sponsor according to the following definition:

[figure not shown]
The test of clinical relevance is that the adverse event in question would cause the Investigator to re-evaluate the risk-benefit assessment of continuing therapy for the patient experiencing the event and to conclude that on a balance of probabilities, the risk-benefit ratio could be materially worsening

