- The decision to expand a minimum of one patient cohort to a 3+3 cohort following a clinically relevant \geq Grade 2 related toxicity will be documented and distributed by the Sponsor to all Investigators as per Section 5.3.4. The decision may occur outside the dose decision meetings as it is dependent on when the event/s occurs. The assessment of a clinically relevant toxicity will end at Week 5 (same as the DLT period i.e. one week post fourth infusion).
- As per Section 9.4, related toxicity will be highly probably, probably and possibly related to BI-1206 (or rituximab in Arm 2).

It should be noted that dose escalation and cohort size decisions will be made based on data from completed cohorts in the single agent arm (Arm 1); available data from the combination arm (Arm 2) will be also be reviewed and considered in the Arm 1 dose decision meetings. Please refer to Section 5.3 for details of the communication plan, the process for dose escalation review and decision making and the dissemination of information.

All patients in a cohort must have completed induction therapy and 7 days post the fourth infusion for dose-escalation to the next cohort to occur. The second patient in any cohort will not commence treatment until after the first patient in that cohort has completed two infusions of BI-1206; the third patient in any cohort will not commence treatment until after the second patient in that cohort has completed one infusion of BI-1206.

Figure 4: Dose escalation decision-making and action if clinically relevant \geq Grade 2 related toxicity and/ or DLT observed at dose levels from Cohort 2 (Part A, Arm 1)

dx = initial dose level dx +1 = 1 level above initial dose

5.4.3 Dose escalation and action if a DLT observed at dose levels from Cohort 2 onwards, Part A, Arm 1

If one instance of DLT is observed in any cohort, the cohort will be expanded to include up to six patients. If one out of the six patients experience a DLT then dose escalation will continue, and the next cohort will consist of a minimum of 3 patients as described in Figure 4. If no DLTs are seen in 3 patients, further escalations will continue as 3+3 cohorts.

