5.9.3 Management of ocular toxicities

As described in Section 2.2.8, preclinical studies noted evidence of Fc γ RIIB expression on the eye. Eye examinations have therefore been included in the schedule of events to allow for assessment throughout study treatment.

If any grade of toxicity affecting the macula and/or affecting patient's vision is observed then study treatment must be stopped and intensified monitoring implemented as per the site ophthalmologist's recommendation. Restarting treatment will be considered on discussion with the PI, CI, ophthalmologist and Sponsor.

If NCI-CTCAE v4.02 Grade 1 ocular toxicity is observed which does not affect the macula or patient's vision, study treatment may continue with intensive monitoring as per site ophthalmologist's recommendation.

If Grade 2 or above ocular toxicity is observed, not affecting the macula or patient's vision, treatment must be stopped and intensified monitoring should be implemented as per site ophthalmologist's recommendation. Restarting treatment will be considered on discussion with the PI/CI, ophthalmologist and Sponsor

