5.9.6 Dose delays and Treatment Discontinuation

In this trial, if a patient experiences one or more of the following toxicities related (highly probably, probably or possibly) to BI-1206 or rituximab treatment, the treatment for that patient should be delayed/modified as described. Please refer to Section 5.9.2 for actions to be taken in event of a reaction during the infusion.

Grade 1 or 2 toxicity (haematological or non-haematological) other than ocular toxicity or infusion related reaction.

No dose modifications or delays are necessary; refer to Section 5.9.3 for guidance on management of ocular toxicity, Section 5.9.2 for guidance on management of infusion related reactions.

Grade 3 or 4 Haematological toxicity that does not meet DLT definition as described in Section 3.3

Treatment with BI-1206 and rituximab, if applicable should be delayed until recovery of the patient's full blood count to Grade ≤ 2 . Treatment may be delayed for a maximum of three weeks. Patients experiencing \geq Grade 3 haematological toxicity lasting longer than three weeks must not receive further treatment with BI-1206 or rituximab. Growth factor support is permissible during this period.

Grade 3 or 4 Non-haematological toxicity that does not meet DLT definition as described in Section 3.3

Refer to Section 5.9.3 for guidance on management of ocular toxicity, Section 5.9.2 for guidance on management of infusion related reactions. For other events, treatment with BI-1206 and rituximab, if applicable, should be delayed until recovery of the AE(s) to Grade ≤ 2 . Treatment may be delayed for a maximum of three weeks. Patients experiencing \geq Grade 3 toxicity lasting longer than three weeks must not receive further treatment with BI-1206 or rituximab.

Please see [Sections 6.2.5.6](#) and [6.2.11.2](#) for further information relating to patient withdrawal from treatment.

Modifications for logistical reasons i.e. Bank Holidays

For logistical reasons (i.e. bank holidays), treatment may be delayed by a maximum of one week or treatment may be given one day earlier (decrease time between dosing to six days during induction therapy) following agreement by CI and Sponsor, prior to commencing treatment.

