5.9.9 Replacement of patients

Patients who come off study due to dose limiting toxicity prior to completing four weeks of induction therapy will not be replaced. Patients who come off study prior to completing four weeks of induction therapy for any other reason will be replaced for purposes of DLT evaluation during the single and combination dose escalation cohorts. Once a RP2D dose has been established (BI-1206 monotherapy and BI-1206 + rituximab combination) patients who withdraw due to disease progression and/or unacceptable toxicity will not be replaced. Other withdrawn patients may be replaced, if considered appropriate, after discussion between the PI, CI and Sponsor.

There may be circumstances based on the emerging data from the trial or IMP availability which result in a patient not being replaced. This will be documented by the Sponsor.

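### The 80% dose rule for DLT evaluability conflicts with the four-administrations rule and is not carried into replacement, escalation or the MTD count

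*Combined protocol and SAP*

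**What the plan says.** **Evaluability.** Section 3.5.3 says that Arm 1 escalation patients "who either receive four administrations of BI-1206 or experience a DLT will be evaluable for dose escalation and/or cohort expansion decisions". Its next paragraph opens "Patients who receive less than 80% of their total planned induction doses (total across the four administrations" and continues that such patients "but complete the DLT period (Week 5) are not evaluable for dose escalation decisions (unless they have experienced a DLT". Section 3.5.4 has the same pair of rules for the combination arm.

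**Replacement.** Section 5.9.9 states: "Patients who come off study prior to completing four weeks of induction therapy for any other reason will be replaced". Patients who leave because of a DLT are not replaced, and the sponsor may document a decision not to replace someone. Footnote b of Table 1 says that cohort size "is also dependant on number of patients that need to be replaced (if patient withdraws for reasons other than DLT". The separate Cohort 1 rule (5.2.1, 5.4) also turns on withdrawal.

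**Escalation.** Section 5.4.2 states: "All patients in a cohort must have completed induction therapy and 7 days post the fourth infusion for dose-escalation". Section 5.5 sets the same condition for Arm 2 and adds absence of DLT. From Cohort 2 the stated minimum is one patient.

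**MTD.** Section 3.4.1 defines the maximum administered dose by two DLTs among up to six patients at a level. It does not say whether those six must be evaluable.

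**The concern.** The MTD or MAD is the Part A primary endpoint, and the recommended dose derived from it is given to up to 25 patients in each Part B arm. A count of DLTs in up to six patients means something only if it is clear who belongs in the six. Sections 3.5.3 and 3.5.4 set an exposure threshold for that purpose, but the sections that act on the count use other tests: leaving the study, or finishing induction.

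The gap matters most because Cohorts 2 to 4 may consist of one patient. In a three-patient cohort, one non-evaluable patient leaves two. In a one-patient cohort, it leaves none.

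**Working it through.** **1. What the plan quantifies.** The documents give no rate of non-evaluable patients, no target DLT rate and no operating characteristics for the escalation rule. The only related figure is the total of up to 81 evaluable patients (Synopsis, 3.2). It reproduces from the Table 1 maxima: 1 + 3 + 3 + 3 + 6 = 16 in Arm 1, and 16 + 15 + 50 = 81. (The Synopsis estimate of 19 for Arm 1 would give 84; that is a separate matter.) So the total is expressed in evaluable patients, whereas the cohort minimum is not.

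**2. Where the 80% line falls.** At a flat dose D the planned total is 4D and the line is 3.2D.
- At 100 mg: planned 400 mg, line 320 mg. Four infusions of 100, 100, 50 and 50 mg total 300 mg, and 300/400 = 75%.
- One infusion missed altogether: 300/400 = 75%.
- Cohort 1: planned 0.4 + 2 + 10 + 50 = 62.4 mg; 80% of this is 49.92 mg. The first three doses supply 12.4 mg, so the patient falls below the line if less than 49.92 − 12.4 = 37.52 mg of the Week 4 dose is given (37.52/50 = 75%).

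**3. Each rule applied to one patient:** four infusions, 75% of planned dose, no DLT, followed to Week 5.

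| Section | Test | Result |
|---|---|---|
| 3.5.3, first rule | four administrations or a DLT | evaluable |
| 3.5.3, second rule | under 80%, DLT period completed, no DLT | not evaluable |
| 5.9.9 | came off study before completing four weeks | no, so not replaced |
| Table 1 footnote b | withdrew | no, so not replaced |
| 5.4.2 | induction completed plus 7 days after fourth infusion | condition met |
| 5.5 (Arm 2 counterpart) | as 5.4.2, without DLT | condition met |
| 3.4.1 | among the up to six | not stated |

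A patient who misses an infusion altogether is different. With no fourth infusion, the literal wording of 5.4.2 is not met.

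**4. Illustration of size.** Let q be the share of patients like the one in step 3. If Cohorts 2, 3 and 4 each run with one patient, independently and with the same q, the chance that at least one has no evaluable patient is 1 − (1 − q)³:
- q = 0.05: 14.3%
- q = 0.10: 27.1%
- q = 0.20: 48.8%

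For a single three-patient cohort the chance of no evaluable patient is q³, or 0.001 at q = 0.10. Every q is an assumption. These figures ignore the toxicity trigger and the dose decision meeting, so they are not a property of the plan.

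**5. Arithmetic for a stronger reading, discussed under the objection.** Under 3+3 a level passes with probability (1 − p)³ + 3p(1 − p)²(1 − p)³. Assume a DLT rate of 0.10 and a related non-DLT stopping rate of 0.20.
- Stops replaced: p = 0.10/(1 − 0.20) = 0.125; passes with probability 0.862.
- Stops kept as patients without DLT: p = 0.10; 0.906.
- Stops counted as if they were DLTs: p = 0.30; 0.494.

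**The case against.** **The two sentences can be reconciled.** The 80% sentence may be meant as an exception to the first. That would settle the classification, but the under-dosed completer would still be outside 5.9.9 and inside the 5.4.2 condition. Or the 80% might refer to the number of infusions: 0.80 × 4 = 3.2, so three or fewer fail and there is no clash. The reference to a total across the four administrations points instead to amount of drug, and on the other reading the sentence would add little to the first.

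**Safeguards exist.** A reader might infer that the plan permits escalation on no evaluable patient. The documents do not go that far.
- Completion is a necessary condition, not a sufficient one, and 3.5.3 itself says such a patient is not evaluable for the decision.
- A clinically relevant related toxicity of Grade 2 or higher in the first patient expands the cohort to at least three (5.4.2), and possibly related events qualify.
- An infusion cut short by an adverse event goes to the sponsor and Chief Investigator (6.2.5.6).
- Escalation needs agreement at the dose decision meeting, which sees safety data from the whole cohort (5.3.1, 5.3.2), and approval by the sponsor's Head of Medical Sciences (5.3.3).
- Figure 4, the decision chart, is not visible in the text available and may count evaluable patients.

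These points reduce the practical risk but do not close the gap. The trigger does not respond to under-dosing for reasons other than toxicity, and the expanded cohort is not counted in evaluable patients either. The explicit promise in 3.5.3 to review non-completers covers those with fewer than four doses, which leaves this patient out.

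**A second stronger reading** is that patients stopped for related non-DLT toxicity vanish from the MTD assessment, so that a poorly tolerated dose is declared tolerated. Such stops exist: under 5.9.6, patients with toxicity of Grade 3 or higher "lasting longer than three weeks must not receive further treatment with BI-1206 or rituximab", and 5.9.3 says "If Grade 2 or above ocular toxicity is observed, not affecting the macula or patient's vision, treatment must be stopped". If these patients leave early without a DLT they are replaced and add no event to the formal count. But ocular stops may be followed by restarting, and delayed patients may complete an extended induction (5.9.7). Cumulative toxicity informs the next dose and the RP2D (3.3), and the MTD and RP2D draw on all relevant toxicity data (3.4.1). Nor does the arithmetic in step 5 show laxity: replacing these patients (0.862) is stricter than keeping them as non-events (0.906). The fall to 0.494 appears only if every related stop is treated as a DLT, which is a wider toxicity definition, not an error in the plan.

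**Conclusion.** The inconsistency stands and should be corrected. On the reading of 80% as amount of drug, 3.5.3 and 3.5.4 classify the same patient two ways. On any reading, the 80% rule is not linked to replacement, the escalation conditions or the MTD denominator. The literal consequence is limited to a patient with four infusions, under 80% of planned dose and no DLT: not replaced, yet meeting the completion condition. In a one-patient cohort this leaves an escalation decision with no evaluable patient, unless the Grade 2 trigger or the dose decision meeting intervenes.

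Its frequency cannot be derived from the documents; the 14% to 49% in step 4 depends wholly on the assumed q and on no safeguard acting. The conclusion also assumes that Figure 4 does not already supply the missing link. It does not extend to the DLT definition, which is not faulted here.

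**What to change.** - Reconcile 3.5.3 and 3.5.4 with 3.4.1, 5.4.2, 5.5, 5.9.9, Table 1 footnote b and Figure 4, so that a single evaluability definition governs who is replaced, how the minimum cohort number is counted and who forms the MTD denominator. State whether the 80% refers to amount of drug or number of infusions. Which definition to adopt is for the sponsor and investigators.
- In the dose-meeting listing and the MTD statement, tabulate for each dose level the treated patients who received under 80% of planned dose because of related toxicity that was not a DLT. This leaves the DLT definition unchanged and adds no second pass criterion.

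**Cost.** Wording in the sections named, one extra listing column and an occasional extra replacement patient. If a share q of patients is non-evaluable, each evaluable place takes on average 1/(1 − q) patients: 1.05 at q = 0.05, 1.11 at 0.10 and 1.25 at 0.20, or 6 × 1.25 = 7.5 treated for six evaluable in the last case. These q values are again assumptions.

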3.5.4 Combination dose escalation decisions (Part A, Arm 2)

The starting dose for BI-1206 in Part A, Arm 2 will not exceed the highest dose of single agent of BI-1206 that has been safely administered in Part A, Arm 1 (at the time of opening Part A, Arm 2), and which is deemed clinically appropriate to combine with rituximab. The starting dose in Part A, Arm 2 will be determined at a dose decision meeting following review of a completed cohort in Part A, Arm 1.

Once Arm 2 is opened, patients treated in the combination dose escalation cohorts who either receive four administrations of BI-1206 in combination with rituximab or experience a DLT will be evaluable for dose escalation and/or cohort expansion decisions in Part A, Arm 2.

Patients who receive less than 80% of their total planned induction doses (total across the four administrations) but complete the DLT period (Week 5) are not evaluable for dose escalation decisions (unless they have experienced a DLT).

Data from all patients who receive less than 4 doses of BI-1206 in combination with rituximab and available data from Part A, Arm 1 will also be reviewed and taken into consideration for subsequent dose escalations in the combination arm. Data from any other trials investigating BI-1206 will also be considered in the dose escalation decisions.

For patients who do not receive the total full dose, please see [Section 5.9.6](#) 'Dose delays/treatment discontinuation' which also offers guidance on the thresholds for re-challenging patients post related AE observation.

3.5.5 Survival

All patients receiving at least one administration of mAb (BI-1206 with/without rituximab) as part of this trial will be evaluable for survival (OS and PFS) regardless of whether they subsequently receive other anti-cancer treatments. Please see Section 7.5.2.

3.6 Study duration

Following completion of recruitment to each escalation arm (single agent or combination) in Part A, the data will undergo review and assessment by the Sponsor. The Sponsor will confirm the decision to progress to Part B of trial and the respective expansion arm (Arm 1 single agent or Arm 2 combination) will open to recruitment. The single agent (Arm 1) and combination (Arm 2) expansion cohorts in Part B may open and progress independently of each other. The Sponsor will confirm when recruitment to each of the expansion cohort is complete.

The number of patients recruited to the dose escalation arms of the study could increase in the event that additional cohorts are required to investigate intermediate doses of BI-1206.

4 PATIENT SELECTION

4.1 Eligibility criteria

The patient must fulfil the eligibility criteria (listed in Sections 4.1.1 and 4.1.2).

4.1.1 Inclusion criteria

1. Written (signed and dated) informed consent and be capable of co-operating with treatment and follow-up.
2. B-cell lymphoma or chronic lymphocytic leukaemia proven by histology or flow cytometry, relapsed or refractory to conventional treatment, or for which no conventional therapy exists or is declined by the patient. Patients should have received at least one line of conventional previous therapy which must have included a rituximab based regimen.
3. Part B only: CD32b positive malignancy as demonstrated centrally by immunohistochemistry or flow cytometry prior to study entry.
4. Life expectancy of at least 12 weeks.
5. World Health Organisation (WHO) performance status of 0-2 (Appendix 1).
6. Haematological and biochemical indices within the ranges shown below to confirm patients eligibility. These measurements must also be performed within one week before their first dose of mAb (BI-1206 and/or rituximab) as part of this study.

Laboratory Test	Value required
Haemoglobin (Hb)	≥ 90 g/L (red cell support is permissible)
Absolute neutrophil count (ANC)	$\geq 1.0 \times 10^9/L$ (or $>0.5 \times 10^9/L$ if due to lymphoma), granulocyte - colony stimulating factor (G-CSF) support is not permissible at screening
Platelet count	$\geq 50 \times 10^9/L$ (or $\geq 30 \times 10^9/L$ if due to malignant involvement of bone marrow)
Serum bilirubin Or: Alanine amino-transferase (ALT) and /or aspartate amino-transferase (AST)	$\leq 1.5 \times$ upper limit of normal (ULN) unless raised due to Gilbert's syndrome in which case up to 3xULN is permissible. $\leq 2.5 \times$ (ULN) unless raised due to malignant hepatic involvement in which case up to 5 x ULN is permissible
Either: Calculated creatinine clearance (Cockcroft Gault) Or: Isotope clearance measurement	≥ 30 mL/min (uncorrected value) ≥ 30 mL/min (corrected)

7. 18 years or over.
8. B-cell lymphoma patients only: patients has at least one measurable lesion by CT scan (defined as greater than 1.5 cm in one axis) or in the case of Waldenström's macroglobulinemia, disease must be assessable by the criteria stated in Appendix 6.
9. **Patients recruited to Arm 2 in Parts A and B (combination arms) only:** CD20 positive malignancy as demonstrated by immunohistochemistry or flow cytometry prior to study entry.

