2.2.8 Expected safety profile for BI-1206 ± rituximab

Based on preclinical experience with BI-1206 alone and in combination with anti-CD20 antibodies (such as rituximab), emerging clinical data from the ongoing CRUKD/16/001 trial, reported clinical data regarding XmAb5871 and clinical experience of rituximab therapy, the potential toxicities associated with BI-1206 ± rituximab therapy could include the following:

- **Infusion related reactions** including CRS are a known, common side-effect of rituximab treatment and are an expected side effect of BI-1206 treatment. Symptoms could include rash, fever, rigors, bronchospasm, and hypotension. All patients will receive supportive care including pre-medication (see Section 5.9.2) and will be monitored before during and after infusion.
- **Side effects resulting from lymphodepletion and/or depletion of immune effector cells**, notably infections related to neutropenia and/or lymphopenia. Neutropenia is considered unlikely based upon the results of preclinical studies undertaken in two murine models that expressed hCD32b and hCD20 under the control of human promoters and on a mCD32b null background. These models demonstrated that BI-1206 ± rituximab selectively depleted B cells preferentially to other lymphoid or myeloid lineage cells. In the event these AE do manifest it is anticipated they will be readily manageable in the context of advanced B-cell malignancies. Haematology assessments conducted during the trial will include assessment of white blood cells (WBC) with differential count (eosinophils, basophils, neutrophils and lymphocytes) and B cell levels. Furthermore, patients who are Hepatitis (Hep) B, C or Human Immunodeficiency Virus (HIV) positive, or who have an active, ongoing infection or an active, known or suspected autoimmune disease will not be eligible for trial participation.
- **Effects on blood pressure**, Blockade of CD32b by BI-1206 could theoretically lead to treatment related changes in blood pressure. Blood pressure will be regularly monitored during the course of the trial and will be managed as required in line with local practice.

- **Thrombocytopenia/platelet count decreased.**
Included due to reported clinical data for the CRUKD/16/001 study. Laboratory test results are regularly monitored during the course of the trial and will be managed in line with local practice. Please see current version of IB for rate of occurrence.
- **Elevated transaminases.**

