3.3 Definition of dose limiting toxicity

Some of the dose limiting toxicity (DLT) and maximum tolerated dose (MTD) definitions are derived from the National Cancer Institute (NCI) Common Terminology Criteria for Adverse Events (CTCAE) Version 4.02. Please note that not all of the events described as DLTs are fully supported by NCI CTCAE but are formed by amalgams of different events in order to assist with assessments of adverse events.

The definition of DLT applies to both the single agent and combination dose escalation arms (Part A of the study [boxes outlined in red in Figure 2]).

A DLT is defined as a highly probably or probably **BI-1206 or rituximab-related AE occurring during** the four weeks of induction treatment and up to one week post the fourth infusion of BI-1206 (i.e. by Day 28/Week 5) which fulfils one or more of the following criteria:

- Neutropenia or neutrophil count decrease Grade 4 ($ANC < 0.5 \times 10^9/L$) for >10 days duration
*see note despite growth factor support
- Febrile neutropenia (fever of unknown origin without clinically or microbiologically documented infection) with Grade 3 or 4 neutropenia (absolute neutrophil count [ANC] $<1.0 \times 10^9/L$) and fever $\geq 38.5^\circ C$).
- Infection (documented clinically or microbiologically) with Grade 3 or 4 neutropenia ($ANC < 1.0 \times 10^9/L$)
- Thrombocytopenia or platelet count decrease Grade 4: a) for ≥ 5 days*see note, or b) associated with active bleeding, or c) requiring platelet infusion
- Grade 3 or 4 non-haematological toxicity. This includes Grade 3 and 4 biochemical AEs as DLTs.

EXCLUDING:

- Grade 3 or 4 nausea or vomiting in patients who have not received optimal treatment with anti-emetics
- Grade 3 or 4 diarrhoea in patients who have not received optimal treatment with anti-diarrhoeals
- Alopecia
- Grade 3 infusion related reactions
- Transient, asymptomatic Grade 3 biochemical abnormalities if agreed by the Sponsor and the study team, including the Chief Investigator
- Event with a fatal outcome.

***Note: In the event of a Grade 4 neutropenia or Grade 4 thrombocytopenia, a full blood count must be performed at least on Day 10 (Day 5 for thrombocytopenia) after the onset of the event to determine if a DLT has occurred. The investigator must continue to monitor the patient closely until resolution to Grade 3 or less. Please See [Section 5.9.4](#) 'Management of thrombocytopenia (Grade 4)' for further details.**

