 - Haematology – haemoglobin (Hb), platelets, white blood cells (WBC) with differential count (eosinophils, basophils, neutrophils and lymphocytes), CD3 T Lymphocytes, CD19 B lymphocytes (usually as part of TBNK or lymphocyte subset panel).
 - Biochemistry – lactate dehydrogenase (LDH), sodium, potassium, calcium (adjusted), phosphate, urea, creatinine, total protein, albumin, bilirubin, alanine aminotransferase (ALT) and/or aspartate aminotransferase (AST)
 - Urinalysis – protein and blood
 - Coagulation–partial thromboplastin time (PTT/APTT) and either prothrombin time (PT) or international normalised ratio (INR).
- Eye examination performed by appropriately trained member of site staff including: slit lamp assessment, retinal examination and measurement of visual acuity (**within four weeks before** the patient receives their first dose of BI-1206 or rituximab on study).

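### Inclusion criterion 6 joins the bilirubin and ALT/AST limits with Or, so as worded one limit is enough, contrary to the criterion's own lead-in, caps and screening panel

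*Combined protocol and SAP*

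**What the plan says.** Criterion 6 in Section 4.1.1 opens by asking for "Haematological and biochemical indices within the ranges shown below to confirm patients eligibility" and then gives a table. One row of that table is labelled "Serum bilirubin Or: Alanine amino-transferase (ALT) and /or aspartate amino-transferase (AST". Its value column holds two limits, each with its own exception:

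- Bilirubin may be up to 1.5 times the "upper limit of normal (ULN) unless raised due to Gilbert's syndrome in which case up to 3xULN is permissible".
- ALT/AST may be up to 2.5 × ULN "unless raised due to malignant hepatic involvement in which case up to 5 x ULN is permissible".

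The next row, on renal function, is labelled "Either: Calculated creatinine clearance (Cockcroft Gault) Or: Isotope clearance measurement" and gives 30 mL/min as the minimum by either method.

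Section 7.1.3 lists the laboratory tests that establish eligibility, to be done within one week before the first dose. Its biochemistry panel includes "albumin, bilirubin, alanine aminotransferase (ALT) and/or aspartate aminotransferase (AST". It states no limits.

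On toxicity, Section 2.2.8 includes "Elevated transaminases" among the potential toxicities and gives clinical data from this study as the reason. Section 3.3 brings Grade 3 or 4 non-haematological toxicity into the DLT definition and adds: "This includes Grade 3 and 4 biochemical AEs as DLTs".

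**The concern.** Bilirubin and transaminases are not two ways of measuring the same thing, yet the row joins them with the connector that the renal row uses for two interchangeable clearance methods. A site that reads the table consistently could take the liver limits as alternatives. A patient with bilirubin in range would then pass the row at any ALT/AST, and a patient with ALT/AST in range would pass at any bilirubin. Another site, following the lead-in, could require both. Each could claim to have followed the protocol.

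At stake is a safety entry threshold in a first-in-human trial of an antibody for which raised transaminases are already listed from the trial's own experience. A liver value that is already high at entry also makes a later rise harder to attribute, and Part A decisions rest on cohorts of one to six patients.

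**Working it through.** No sample size, error rate or event count is involved, so the check is one of logic and of reading the sections against each other.

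**Step 1. The two readings.** Take the inputs from the criterion 6 table: bilirubin within its limit (yes/no) and ALT/AST within its limit (yes/no), each including its stated exception.

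| Bilirubin | ALT/AST | One limit suffices (as worded) | Both limits needed |
|---|---|---|---|
| in | in | pass | pass |
| in | out | pass | fail |
| out | in | pass | fail |
| out | out | fail | fail |

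The readings differ in two of the four cells, namely every patient with exactly one abnormality beyond its limit. As an assumed illustration, take bilirubin 1.0 × ULN with ALT 8 × ULN. The ALT is 8 / 2.5 = 3.2 times the general limit and 8 / 5 = 1.6 times the cap for malignant liver involvement, but the row as worded is satisfied.

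**Step 2. Lead-in.** It calls for the indices to lie within the ranges shown. Both tests have a range in the table. Nothing in the lead-in says that one may be ignored if the other is met.

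**Step 3. The caps.** If one limit suffices, the Gilbert's allowance (1.5 to 3 × ULN) decides eligibility only when ALT/AST is out of range, because otherwise the patient has already passed. Likewise, the liver-involvement allowance (2.5 to 5 × ULN) decides only when bilirubin is out of range. If both limits apply, each allowance does its natural work. The caps therefore point to both being intended.

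**Step 4. Screening panel.** Section 7.1.3 requires bilirubin and at least one transaminase from every patient for eligibility. That fits a plan to apply both limits, but the section sets no threshold and so does not settle the matter.

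**Step 5. Other criteria.** No other inclusion or exclusion criterion sets a numeric liver limit. The nearest are:

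- Exclusion 7 covers persisting toxicity from earlier treatment.
- Exclusion 11 covers patients at high risk from systemic illness other than the malignancy.
- Exclusion 12 covers known viral hepatitis and HIV.
- Exclusion 17 is investigator judgement.

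A high ALT caused by lymphoma in the liver would fall outside 7, 11 and 12, leaving only 17.

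**Step 6. Link to DLTs.** Transaminases are not named in Section 3.3. They enter through the general clause on biochemical events. A Grade 3–4 rise counts only if it falls in the DLT window and in one of the top two causality categories. Short-lived, symptom-free Grade 3 changes can be set aside by agreement.

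**The case against.** The best case for the plan is that this is a drafting slip that few investigators would exploit. The liver row has no Either, whereas the renal row, where alternatives are plainly meant, prints both words. The lead-in, the caps and the panel all suggest that both limits apply. There are also other barriers: exclusions 7, 11, 12 and 17, sponsor registration of each patient before treatment (Section 4.2), and biochemistry review before every infusion (Section 7.2). Most of this stands, and it is why the point is an internal contradiction and not a deliberate design choice. It does not remove the printed connector, and none of the barriers supplies a number.

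A reader might infer three stronger things that the documents do not support.

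- *That the trial admits patients at any ALT.* The wording passes such a patient through this row only; the other exclusions and registration may still stop them.
- *That a misattributed liver DLT would expand a cohort or end escalation.* Section 5.4.3 does expand a cohort after one DLT, and Section 5.6 does stop escalation after two. But the causality definitions in Section 9.4 ask whether the patient's own condition or another medical cause explains the event, so a documented baseline elevation bears directly on the call. DLTs are also agreed at a dose decision meeting (Section 5.3.2). Misattribution is possible, but no frequency can be derived.
- *That every transaminase measured must be in range.* The and/or wording leaves this open, and the same phrase in Section 7.1.3 is consistent with sites that measure one enzyme. No such rule appears in the documents.

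**Conclusion.** The contradiction is real. As worded, the row passes a patient who meets only one of the two liver limits, while the lead-in, the separate exceptions and the eligibility panel indicate that both were meant. No other criterion supplies a numeric limit, although partial and discretionary cover exists.

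The size can be stated only in logical terms: the two readings disagree for every patient with exactly one of the two tests beyond its limit. The documents do not say how many such patients would be screened, so no proportion can be given. Any effect on DLT attribution, and through it on the MTD or RP2D, is a plausible inference that cannot be quantified. The conclusion assumes that the connector is printed text in the table, as its underlining suggests. The point deserves correction because it concerns a safety entry threshold for a toxicity already listed from this trial, and because the correction is cheap.

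**What to change.** Reconcile the row with its lead-in and state explicitly whether both liver limits must be met. If both are intended, remove the connector and print bilirubin and ALT/AST as two separate rows, each keeping its existing limit and exception. If one limit is truly meant to suffice, say so and explain how that fits the lead-in and the caps. In either case, state how the ALT/AST limit applies when both enzymes have been measured.

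The cost is a short eligibility amendment. No limit changes and no test is added, since Section 7.1.3 already requires both kinds of measurement. If both limits are confirmed, a few patients with an isolated liver abnormality who pass the row as now worded would fail screening.
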